3.2 BENEFITS

There are no guaranteed benefits from participation in this clinical investigation. Aortic valve replacement with the EDWARDS INTUITY Aortic Valve may result in one or more of the following benefits: improved valvular function, acute alleviation of symptoms related to aortic stenosis, and/or improved morbidity and mortality.

Additionally, information gained from the conduct of this investigation may be of benefit to other people with the same medical condition in the future. The long-term results of using the investigation valve are not known at the present time. Alternative treatments may include palliative medical therapy, aortic balloon valvuloplasty and replacement of the aortic valve with prosthesis other than the EDWARDS INTUITY Aortic Valve.

Edwards developed the EDWARDS INTUITY Valve System, INTUITY Aortic Valve Models 8300ACA and 8300ACB to facilitate less invasive surgical approaches requiring fewer suture placements.

The Models 8300ACA and 8300ACB valve use the commercially available Magna Ease valve with a modified balloon expandable annular frame. The Models 8300DCA and 8300DCB delivery system allows for less invasive valve replacement.

The potential advantage of the Models 8300ACA and 8300ACB design is a balloon expandable frame reducing the number of sutures required without increasing the risk for paravalvular leak.

4 CLINICAL INVESTIGATION DESIGN

This is a two-phase, non-randomized, prospective, single arm, multi-center clinical investigation.

4.1 PHASE I

In **Phase I**, a total of 10 subjects will be enrolled at up to 2 participating investigational centers. Safety data will be reviewed by the Data Monitoring Committee (DMC) after 10 subjects have completed 1-month follow-up⁵. Following recommendation by the DMC, enrollment will proceed to Phase II. (Refer to Section 14.1 for DMC.)

4.2 PHASE II

In **Phase II**, 340 additional subjects will be enrolled in up to 8 participating investigational centers. Combined enrollment in Phase I and Phase II of this investigation will be 350 subjects.

Each subject in Phase I and Phase II is consented for a period of 5 years. All subjects will be assessed for clinical follow-up at the following intervals: Discharge, 1 month, 3 months, 1 year and annually thereafter until 5 years of follow-up is achieved per subject.

5 ENDPOINTS

5.1 SAFETY ENDPOINTS

The following primary safety endpoints will be assessed throughout each subject's participation in the investigation:

- Study valve-related mortality
- Thromboembolic events
- Study valve thrombosis
- Major bleeding events
- Study valve paravalvular leakage
- Study valve-related endocarditis

In addition, the following safety endpoints will also be assessed throughout each subject's participation in the investigation:

- All-cause mortality
- Study valve structural valve deterioration
- Hemolysis
- Study valve-related reoperation
- Study valve explant
- All adverse events

⁵ This may include subjects who expired or had the valve explanted prior to 1 month.

5.2 PERFORMANCE ENDPOINTS

The following performance endpoint will be assessed when the investigation procedure is performed:

 Device technical success (successful delivery and deployment of one bioprosthesis with one delivery system)

The following performance endpoint will be determined when the subject is discharged from the hospital or 10 days post implant, whichever occurs first:

 Procedure success defined as device technical success followed by the absence of adverse events requiring device reoperation, requiring implantation of permanent pacemaker (with baseline sinus rhythm and no other conduction issues), or subject death

The following performance endpoints will be assessed at each scheduled follow-up visit:

- Improvement in NYHA functional class
- Hemodynamic performance (mean gradient, effective orifice area, regurgitation by echocardiogram).

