Potential Risks associated with EDWARDS INTUITY Aortic Valves and Delivery Systems may be found in the respective IFU. Based on a review of scientific literature, preliminary animal studies, risk analysis and a Failure Modes and Effects Analysis (FMEA) potential risks associated with the use of the EDWARDS INTUITY Aortic Valves may include:

- Loss of frame structural integrity resulting in damage to aortic wall or aortic annulus
- Delivery system impingement resulting in mitral chordae trauma or damage
- Frame damage or flaring resulting in a reduction of effective orifice area
- Hemolysis
- Frame expansion resulting in conduction interruptions or disturbances (i.e. arrhythmia)
- Frame expansion resulting in mitral valve impingement or abrasion with or without mitral regurgitation
- Insufficient frame expansion/suturing resulting in paravalvular leak requiring intervention or reoperation to resolve
- Device malpositioning resulting in ostial blockage
- Device embolization into the aorta/ventricular due to suture failure

Some or all of these risks could require a need for reoperation or explant, and may lead to permanent disability or death.

There may be other risks that are unknown at this time. All safety events will be collected and reviewed throughout the entire investigation and follow-up period. Investigators will be notified of any additional risks identified that could affect the health, safety or welfare of the investigation subjects.

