12.2 SAMPLE SIZE PHASE II

Phase II will enroll up to 340 subjects. The sample size is determined based on ISO5840 requirements. The rational for the increase is based on estimation of the number of additional subjects required in order to reach a minimum of eight subjects implanted with the smallest valve size tested (19 mm valves) and a minimum of fifteen subjects implanted with the larger 27mm valve size tested to met ISO5840 requirements.

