12.4 PHASE II ANALYSIS

12.4.1 ANALYSIS POPULATION

The primary safety analysis will include all the enrolled subjects including those enrolled in Phase I. The performance analysis will include the subjects who survived at least 30 days post implant.

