12.4.3 PERFORMANCE ANALYSIS

The device technical success and procedure success will be summarized by counts and percentages.

Subjects will be analyzed according to the NYHA classification preoperatively, at 3 months and annually post implant for 5 years. The distribution (numbers of subjects and percentages) in the various NYHA classes will be tabulated at each follow-up interval.

Echocardiography data will be obtained preoperatively, at discharge (or 10-days post implant, whichever occurs first), at 6-months and at 1, 3, and 5 year follow-ups. Descriptive statistics for the continuous echo variables and change from baseline (e.g. mean, standard deviation, and range) will be categorized by time interval and size. Regurgitation data will be summarized using frequency at each severity level.

Improvement in regurgitation at one year will be analyzed via the Wilcoxon Signed-Rank test. Change at one year from baseline for all other hemodynamic outcomes will be analyzed using paired *t*-tests.

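### Procedure success is observed to discharge or day 10, whichever is first, so the window varies by subject and center; separately, the 30-day-survivor population removes every death that the definition counts as a failure.

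*Combined protocol and SAP*

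**What the plan says.** Section 5.2 defines the endpoint as follows: "Procedure success defined as device technical success followed by the absence of adverse events requiring device reoperation, requiring implantation of permanent pacemaker", or death. The pacemaker component applies only to subjects "with baseline sinus rhythm and no other conduction issues". Status is fixed when the subject is "discharged from the hospital or 10 days post implant, whichever occurs first". Section 9.4.2 confirms the cap: a subject still in hospital at day 10 has an echocardiogram at that point to complete the evaluation.

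On the population, Section 12.4.1 states: "The performance analysis will include the subjects who survived at least 30 days post implant". On the analysis, Section 12.4.3 states: "The device technical success and procedure success will be summarized by counts and percentages". No interval, test or performance goal is attached.

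Elsewhere, Section 3.1 lists this device risk: "Frame expansion resulting in conduction interruptions or disturbances (i.e. arrhythmia"). Section 5.1 follows all-cause mortality, valve-related reoperation, explant and all adverse events throughout participation. Pacemaker implantation is not a named safety endpoint. New or worsening conduction disturbance is collected under other data (Section 5.3), and Section 12.4 describes no analysis of it.

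**The concern.** The observation window is not the same for every subject. Take two subjects who each need a pacemaker on day 7. One went home on day 5 and is a success; the other is still in hospital and is a failure. With up to 8 Phase II centers, differences in discharge practice feed directly into the percentage, and a center with shorter stays looks better for the same clinical course.

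This matters most for the pacemaker component. Conduction disturbance is a recognised risk of expanding the frame, and the purpose of the study is to show that the frame does no harm. Yet this is the component with the least cover elsewhere in the analysis plan.

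The death component has a different fault. Any death that the definition counts occurs by day 10, and the survivor restriction then takes that subject out of the analysis.

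**Working it through.** **1. Figures in the plan.** The documents state no expected procedure success rate, goal, margin, length of stay or event timing, so there is no figure for this endpoint to reproduce. The nearby enrollment total agrees: 10 + 340 = 350.

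**2. Direction of the window effect.** For subject *i* the cut-off is T = min(discharge day, 10), which is at most 10. Every failure by T is also a failure by day 10, but not the reverse. In the same subjects, the success percentage as defined is therefore equal to or higher than the fixed day-10 percentage. It can never be lower.

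**3. Size of the window effect (pacemakers).** All three inputs are assumptions, because the documents give none of them:

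- p = share needing a permanent pacemaker by day 10: 4 to 8%
- L = share of those pacemakers placed after discharge: 10 to 30%
- s = share of subjects not in baseline sinus rhythm, who cannot fail on this component: 10 to 25%

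Fall in the rate under a fixed day-10 window = p × L × (1 − s).

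- Low: 4% × 10% × 75% = 0.30 points; 0.0030 × 350 = about 1 subject
- High: 8% × 30% × 90% = 2.16 points; 0.0216 × 350 = about 8 subjects

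This assumes that pacemaker need does not depend on baseline rhythm, that no subject is excluded for another conduction issue alone, and that none of these subjects has already failed for another reason. Device reoperations between discharge and day 10 would add to it.

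**4. How deaths are scored.**

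| Time of death | Section 5.2 | Section 12.4.1 | Net result |
|---|---|---|---|
| Before the cut-off | Failure | Excluded | Not counted |
| Cut-off to day 30 | Not a failure | Excluded | Not counted |
| After day 30 | Not a failure | Included | Scored on the early course |

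The cut-off is never later than day 10, so the death component is always empty in the planned analysis.

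**5. Size of the population effect (illustration).** Let m = 30-day mortality. Take 2 to 8%, borrowing the operative mortality range cited in Section 3.3. Let a = 5% non-fatal failures before the cut-off, assumed to fall among 30-day survivors, and f = 25 to 50% of the 30-day deaths occurring after the cut-off; both are assumptions. Subjects dropped: 0.02 × 350 = 7 to 0.08 × 350 = 28.

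- As planned (survivors): (1 − m − a)/(1 − m)
- Same cut-off, all enrolled: 1 − a − m(1 − f)

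| m | As planned | All enrolled | Gap (points) |
|---|---|---|---|
| 2% | 93/98 = 94.9% | 93.5 to 94.0% | 0.9 to 1.4 |
| 5% | 90/95 = 94.7% | 91.2 to 92.5% | 2.2 to 3.5 |
| 8% | 87/92 = 94.6% | 89.0 to 91.0% | 3.6 to 5.6 |

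The planned figure barely moves while mortality quadruples. On these inputs the survivor restriction can matter more than the window.

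**The case against.** The best defence is that the percentage is right for the endpoint as defined; it is high only relative to a longer, common window. Nothing formal rests on it. Section 2.2.1 makes success a Data Monitoring Committee judgement, Section 12.4.3 is descriptive, and on the number of subjects Section 12.2 says: "The sample size is determined based on ISO5840 requirements". Deaths, reoperations and explants have their own reporting in Sections 5.1 and 12.4.2. Section 9.4.1 recommends at least five days of telemetry, which suggests several days of early observation, so few events may fall between discharge and day 10. All of this stands, and it keeps the point minor. It does not remove the dependence on discharge practice: five days is only a recommendation and is shorter than ten. Nor does it give later pacemakers a named summary.

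Two stronger readings are tempting. First, a reader might infer that early discharge turns later deaths into successes. It does not for any death before day 30, because Section 12.4.1 excludes those subjects. Second, a reader might add all uncounted pacemakers together: 4% − 4% × 90% × 90% = 0.76 points, up to 8% − 8% × 70% × 75% = 3.8 points. That total includes pacemakers in subjects outside the baseline-rhythm qualifier. The qualifier is a deliberate part of the definition and not a product of the window, and a fixed window would leave those pacemakers uncounted.

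**Conclusion.** The point holds as a minor one. The window varies by subject and center, and it can only raise the success percentage relative to a fixed day-10 window in the same subjects. On the assumed inputs the difference is about 0.3 to 2.2 points, or roughly 1 to 8 of 350 subjects. Since the documents give no pacemaker rate, length of stay or event timing, the true figure could be close to zero.

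The conflict between Sections 5.2 and 12.4.1 over deaths does not depend on any assumed rate: a stated failure component can never be observed. Only its size is illustrative.

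The documents do not support a claim that the trial's conclusion is compromised, because no success criterion uses this figure.

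**What to change.** - **Sections 5.2 and 12.4.3:** count the failure events through day 10 for every subject, whether or not discharged earlier. The discharge-based figure may stay as a secondary line.
- **Section 12.4.1:** analyse procedure success in all enrolled subjects, so that deaths count as the definition says, and reconcile this section with Section 5.2.
- **Section 12.4.3:** also show the pacemaker component over subjects at risk for it, that is, those in baseline sinus rhythm with no other conduction issue.

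The cost is wording and a re-derived flag. Adverse events are collected from consent (Section 9.3), reported as they occur (Section 11.1) and recorded at the 1-month contact (Section 9.4.3), so no visit or test is added. The downside is a lower reported success rate: slightly lower from the window, and further lower from counting deaths, by an amount that depends on early mortality.

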5.3 OTHER DATA

The following data also will be collected:

- EQ-5D Quality of Life questionnaire at baseline, 3-months and 1-year only,
- Blood data (White Blood Cell Count, Red Blood Cell Count, Hemoglobin, Hematocrit, Haptoglobin, Reticulocytes, Platelet Count, Serum Lactate Dehydrogenase) at baseline, 3-months, 1- and 5-years only,
- New onset or worsening of conduction disturbances.

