6.2 PRE-OPERATIVE CRITERIA

6.2.1 INCLUSION CRITERIA

The principal investigator at the investigational center has the responsibility of screening potential subjects to determine if the subjects meet all the inclusion criteria. The following are requirements for entry into Phase I or Phase II of the clinical investigation:

- 1. Subject is 18 years or older
- 2. Subject has a ortic stenosis or stenosis-insufficiency of an aortic valve requiring a planned replacement as indicated in the preoperative evaluation.

- 3. Subject is scheduled to undergo planned aortic valve replacement with or without concomitant coronary bypass surgery, MAZE procedure, septal myectomy, pacemaker/ICD implant and or atrial appendage occlusion/removal.
- 4. Subject has signed and dated the investigation informed consent form prior to investigation procedures.
- 5. Subject is geographically stable and agrees to attend follow-up assessments at the hospital of surgical services for a maximum of 5 years.

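### Procedure success counts a new pacemaker as a failure only in subjects with normal baseline rhythm and conduction, reports it over a wider population, and is not backed by any separate pacemaker rate

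*Combined protocol and SAP*

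**What the plan says.** - **Definition (section 5.2, repeated in the synopsis).** Procedure success is device technical success with no later adverse event leading to device reoperation, a pacemaker or death. The last two components read "requiring implantation of permanent pacemaker (with baseline sinus rhythm and no other conduction issues), or subject death". Status is fixed when the subject is "discharged from the hospital or 10 days post implant, whichever occurs first".
- **Who can enter (section 6.2.1, inclusion criterion 3).** Concomitant procedures may include MAZE, "septal myectomy, pacemaker/ICD implant and or atrial appendage occlusion/removal". None of the exclusion criteria in section 6.2.2 concerns atrial fibrillation, bundle branch or AV block, or an existing pacemaker. Section 9.4.1 itself foresees subjects who are not in sinus rhythm.
- **Analysis (section 12.4.3).** "The device technical success and procedure success will be summarized by counts and percentages". No at-risk denominator and no breakdown by component is given.
- **Populations (section 12.4.1).** "The performance analysis will include the subjects who survived at least 30 days post implant". By contrast: "The primary safety analysis will include all the enrolled subjects including those enrolled in Phase I".
- **Device risk (section 3.1).** Among the risks tied to this valve: "Frame expansion resulting in conduction interruptions or disturbances (i.e. arrhythmia".
- **Other capture.** Section 5.1 lists all adverse events as a safety endpoint. Section 5.3 collects, as other data, "New onset or worsening of conduction disturbances". Section 12 names no summary of conduction disturbance or of pacemaker implantation.

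**The concern.** The numerator rule and the denominator do not match. Subjects outside sinus rhythm, or with any other conduction problem, cannot fail on the pacemaker component, yet they stay in the percentage. If such a subject develops block from frame expansion and needs a pacemaker, procedure success records a success.

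This matters because the stated purpose (section 2.2) is to confirm that adding the expandable frame does no harm to safety or performance, and conduction disturbance is one of the frame's named risks. Procedure success is the only endpoint that mentions pacemakers. As planned, its pacemaker component depends on the baseline rhythm mix of the enrolled subjects as well as on the device.

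The denominator has a second problem. The endpoint closes by day 10 at the latest, while the performance population requires survival to day 30. Every death that section 5.2 would score as a failure is removed before the percentage is formed.

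**Working it through.** **The plan's own figures.** Enrollment adds up: 10 + 340 = 350. The documents state no expected rate, target or test for procedure success or for pacemakers, so there is nothing else to reproduce.

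**Inputs**
- f: share of the performance population that can fail on the pacemaker component. Not in the documents; assumed 0.6 to 1.0.
- r: new pacemaker rate in that share. Not in the documents; assumed 5% and 10%.
- q: new pacemaker rate in exempt subjects who have no existing or planned device. Not in the documents; assumed 10% to 20%.
- d: share of exempt subjects who do have an existing or planned device. Not in the documents; shown at 0 and 0.5.
- Operative mortality of 2 to 8%, which section 3.3 cites for valve replacement at most centers. It is used here as a stand-in for 30-day mortality.

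**Step 1: dilution of the component.** Reported component = f × r. At-risk rate = r. Relative understatement = 1 − f, whatever r is.

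| f | Reported, r = 5% | Reported, r = 10% | Relative understatement |
|---|---|---|---|
| 1.0 | 5.0% | 10.0% | 0% |
| 0.9 | 4.5% | 9.0% | 10% |
| 0.8 | 4.0% | 8.0% | 20% |
| 0.7 | 3.5% | 7.0% | 30% |
| 0.6 | 3.0% | 6.0% | 40% |

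**Step 2: pacemakers scored as successes.** Number = N × (1 − f) × (1 − d) × q. Take N = 350 and f = 0.8.
- Counted as failures at r = 10%: 350 × 0.8 × 0.10 = 28 (8.0%).
- Exempt subjects: 350 × 0.2 = 70.
- Uncounted with d = 0: 70 × 0.10 = 7 to 70 × 0.20 = 14.
- Uncounted with d = 0.5: 3.5 to 7.

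The factor (1 − d) is needed because an exempt subject who already has, or is due to receive, a device is not a candidate for an uncounted new one.

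**Step 3: the survivor denominator.** At 2 to 8% mortality, 350 × 0.02 = 7 to 350 × 0.08 = 28 subjects leave, so 343 to 322 remain. The relative dilution in step 1 depends only on f. At f = 0.8, d = 0 and q = 10%, the uncounted number becomes 343 × 0.2 × 0.10 = 6.9 to 322 × 0.2 × 0.10 = 6.4.

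**Step 4: deaths removed.** Suppose all other failures are 5% of survivors (assumed). Success in survivors is 95.0%. If every removed death counted as a failure, success in all enrolled would be 343 × 0.95 / 350 = 93.1% or 322 × 0.95 / 350 = 87.4%. The gap of 1.9 to 7.6 points is an upper bound for these inputs, because deaths after discharge or day 10 are not failures under section 5.2.

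**The case against.** The case for leaving the plan alone has real strength.

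- **Attribution.** Limiting pacemaker failures to subjects with a normal baseline is a defensible way to isolate device effects. Exempt subjects can still fail on technical success or reoperation, so they belong in the composite's denominator. This stands: the composite percentage is not wrong, and the definition need not change. What is missing is a component rate with its own denominator.
- **Capture elsewhere.** A reader might infer that conduction harm goes unrecorded outside this endpoint. The documents do not support that. Adverse events are a safety endpoint in all enrolled subjects, section 5.3 collects conduction disturbance with no rhythm exemption, and section 12.4.2 plans early percentages and late rates for other complications. What remains is that no pacemaker or conduction line is named, so its definition and denominator would be chosen after the data are in.
- **Existing or planned devices.** A reader might infer that these subjects hide failures. They are weak examples. Someone with a pacemaker does not ordinarily need one implanted, and a planned implant is not required by an adverse event. The concern rests on baseline atrial fibrillation and conduction disease.
- **Denominator.** A reader might infer that the percentage is taken over everyone enrolled. Section 12.4.1 says 30-day survivors. Nor does that rule hide early deaths from the trial, since all-cause mortality is a safety endpoint and the primary safety analysis keeps all enrolled subjects. It removes them only from procedure success.
- **Site behavior and vulnerability.** Nothing in the documents shows that centers would exempt subjects for trivial ECG findings, or that prior conduction disease raises the risk from the frame. The event codes and the events committee's charter are not included. Neither point is relied on here.
- **Consequence.** The endpoint is descriptive. Section 12.2 bases the sample size on valve-size minimums, and Phase II success is the data monitoring committee's judgment on 3-month data (section 2.2.1). No error rate or decision rule changes.

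**Conclusion.** The point holds as a reporting gap. Procedure success includes subjects who cannot fail on its pacemaker component and scores their new pacemakers as successes if nothing else fails. No planned table shows the at-risk rate or the overall new-pacemaker rate. The direction needs no assumption: any exempt share above zero puts the component below the at-risk rate. The size cannot be known from the documents. It is 10 to 40% relative for an assumed at-risk share of 0.9 to 0.6, and zero if nobody is exempt.

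Separately, sections 5.2 and 12.4.1 conflict on early deaths: one defines them as failures and the other removes them. Both matters affect how a descriptive result on a named device risk is read. This is a change that should be made, but it does not threaten the trial's conclusions.

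**What to change.** Keep the composite as defined in section 5.2 and add to section 12.4.3:

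1. The pacemaker component as a percentage of subjects in sinus rhythm at baseline with no conduction disease and no existing or planned device, with that denominator stated.
2. New permanent pacemaker as a percentage of all enrolled subjects with no existing or planned pacemaker/ICD, whatever the baseline rhythm. Show it overall, by baseline rhythm and conduction status, and with and without concomitant MAZE or septal myectomy. State the time window.

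Set baseline status from the pre-implant 12-lead ECG and the surgical plan.

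State the denominator for procedure success and reconcile it with section 12.4.1. Using all enrolled subjects would let deaths by discharge or day 10 count as failures, as section 5.2 intends.

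The cost is a little more table work and a slightly less favorable reported rate. Baseline ECG and previous procedures (Table 1), concomitant procedures (Table 2), and discharge ECG and adverse events (Table 3) are already collected. The endpoint definition, the tests and the sample size do not change.
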